5.4.2. QTc Stopping Criteria

- The *same* QT correction formula *must* be used for *each individual subject* to determine eligibility for and discontinuation from the study. This formula may not be changed or substituted once the subject has been enrolled.
 - For example, if a subject is eligible for the protocol based on the corrected QT interval using the Fridericia formula, then the corrected QT interval using the Fridericia formula must be used for discontinuation of this individual subject as well.
 - Once the QT correction formula has been chosen for a subject's eligibility, the *same formula* must continue to be used for that subject *for all QTc data being collected for data analysis*. Safety ECGs and other nonprotocol specified ECGs are an exception.
- The QTc should be based on single or averaged QTc values of triplicate ECGs obtained over a brief (e.g., 5 to 10 minute) recording period.

A subject who meets either of the bulleted criterion below will be withdrawn from the study:

- QTcF >500 msec
- Change from baseline of QTc >60 msec

For patients with underlying **bundle branch block**, follow the discontinuation criteria listed below:

Baseline QTc with Bundle Branch Block	Discontinuation QTc with Bundle Branch Block
<450 msec	>500 msec
450 to 480 msec	≥530 msec

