4.3. Type and Number of Subjects

In Part 1, up to 16 subjects with normal renal function will be matched to approximately 8 subjects with moderate renal impairment, and approximately 8 subjects with severe renal impairment and/or subjects with ESRD not on hemodialysis for a total of approximately 32 subjects. In Part 2 (optional), approximately 4 to 8 subjects with normal renal function (if enrolled), approximately 4 to 8 subjects with mild renal impairment, and approximately 4 to 8 subjects with ESRD on hemodialysis will be enrolled for a total of approximately 12 to 24 subjects.

If there are a sufficient number of subjects with normal renal function enrolled in Part 1 (Group A) that match subjects with renal impairment in other groups, a determination will be made regarding enrollment of matching subjects with normal renal function in Part 2 (Group D). In addition, if subjects prematurely discontinue the study, additional replacement subjects may be enrolled at the discretion of the Sponsor in consultation with the investigator.

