4.6.1. Risk Assessment

Potential Risk of Clinical Significance	Summary of Data/Rationale for Risk	Mitigation Strategy
Investigational Product (IP) Gepotidacin		
Gastrointestinal (GI) Effects	
Lower GI effects (soft stools, flatulence, and diarrhoea) are the most common GI-associated adverse events (AEs) reported in human subjects dosed with gepotidacin.
 
In the Phase I studies, out of approximately 400 healthy subjects who have received gepotidacin, C. difficile has been reported in 8 subjects.
	
Exclusion criterion and close monitoring of clinical parameters and AEs will be conducted to mitigate and assess GI effects.
 
Patients with significant GI symptoms will obtain the appropriate work-up (Appendix 8).
 
Subject stopping criteria: Subjects experiencing Grade 3 or Grade 4 AEs will have permanent discontinuation of the investigational medication and will be followed as appropriate until resolution of the AE.

Cardiovascular Effects Reversible increase in QT prolongation and a mild increase in heart rate in human subjects.	In Study BTZ115775 [see GlaxoSmithKline Document Number 2015N227098_00 Study ID BTZ115775], the infusion of gepotidacin at a dose of 1000 mg and 1800 mg over 2 hours caused a mild heart rate effect of approximately 6 bpm to 10 bpm and a QT prolongation, measured as $\Delta\Delta\text{QTcF}$, of 12 msec to 22 msec. The QT prolongation evolved during the infusion and was quickly reversed over 2 hours after the end of the infusion. Blood pressure observations were within normal ranges.	
Exclusion criteria, close monitoring of clinical parameters, and AEs will be conducted and stopping criteria will be utilized to mitigate and assess cardiovascular effects.
 
Note: Subjects with a QRS duration <70 and >120 msec will be excluded.
 
Subject stopping criteria: Subjects experiencing a QTcB and/or QTcF >500 msec and/or a change from baseline in QTc >60 msec.

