uses heparin to maintain IV cannula patency).

CONCOMITANT MEDICATIONS

12. Subject has used medications known to affect the elimination of serum creatinine (e.g., trimethoprim or cimetidine) or competitors of renal tubular secretion (e.g., probenecid) within 30 days before dosing.
13. Subjects cannot use any over-the-counter, or prescription medication (except for hormonal contraceptives and/or acetaminophen; see Section 6.11 for more details), vitamin supplement, or herbal medication within 7 days (or 5 half-lives, whichever is longer) before dosing and during the study within 7 days before dosing and during the study. Any exceptions (including subjects with renal impairment that will be on medications during the study) will be discussed with the sponsor or medical monitor on a case-by-case basis and the reasons will be documented.

DIAGNOSTIC ASSESSMENTS AND OTHER CRITERIA

14. Subjects with normal renal function have a presence of hepatitis B surface antigen or positive hepatitis C antibody test result at Screening or within 3 months prior to first dose of study treatment. A subject with renal impairment with stable hepatitis C who has normal liver function test results is allowed with investigator approval.
15. A positive test for human immunodeficiency virus antibody.
16. Subject has clinically significant abnormal findings in serum chemistry, hematology, or urinalysis results obtained at Screening or Day -1 (and Day 7 for Group F only), other than those associated with underlying renal conditions or other stable medical conditions consistent with the disease process.
17. Subject with normal renal function has a baseline corrected QT interval using the Fridericia formula (QTcF) of >450 milliseconds (msec) and subject with renal impairment has a baseline QTcF of >480 msec.

OTHER EXCLUSION CRITERIA

18. Donation of blood in excess of 500 mL within 12 weeks prior to dosing or participation in the study would result in donation of blood or blood products in excess of 500 mL within a 56 day period.
19. Previous exposure to gepotidacin within 12 months prior to the first dosing day.
20. The subject has participated in a clinical trial and has received an investigational product within the following time period prior to the first dosing day in the current study: 30 days, 5 half-lives, or twice the duration of the biological effect of the investigational product (whichever is longer).

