5.4. Withdrawal/Stopping Criteria

The following actions must be taken in relation to a subject who fails to attend the clinic for a required study visit:

- The clinic must attempt to contact the subject and reschedule the missed visit as soon as possible.
- The clinic must counsel the subject on the importance of maintaining the assigned visit schedule and ascertain whether or not the subject wishes to and/or should continue in the study.
- In cases where the subject is deemed “lost to follow-up”, the investigator or designee must make every effort to regain contact with the subject (where possible, 3 telephone calls, emails, or text messages; and, if necessary, a certified letter to the subject’s last known mailing address or local equivalent methods). These contact attempts should be documented in the subject’s medical record.
- Should the subject continue to be unreachable, only then will he/she be considered to have withdrawn from the study with a primary reason of “lost to follow-up.”

A subject may withdraw from study treatment at any time at his/her own request, or may be withdrawn at any time at the discretion of the investigator for safety, behavioral, or administrative reasons. If a subject withdraws from the study, he/she may request destruction of any samples taken, and the investigator must document this in the clinic study records.

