5.4.1. Liver Chemistry Stopping Criteria

Liver chemistry stopping and increased monitoring criteria have been designed to assure subject safety and evaluate liver event etiology in alignment with the FDA guidance, “Drug-Induced Liver Injury: Premarketing Clinical Evaluation,” [DHHS, 2009].

Study treatment will be stopped if the following liver chemistry stopping criterion is met:

- $ALT \geq 3 \times ULN$

Although stopping criteria for continued dosing of investigational product due to liver chemistry parameters are not applicable for single-dose studies, and, in this case, for subjects that will receive the gepotidacin dose twice (Group F), if subjects are found to have values consistent with usual stopping parameters, it is appropriate to institute evaluation and monitoring criteria according to standard GSK criteria. Therefore, liver

function tests should be evaluated according to stopping criteria and work-up instituted if defined parameters are reached.

For details of the required assessments if a subject meets the above criteria, refer to [Appendix 2, Liver Chemistry Follow-up Procedures](#).

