5.4.3. Gastrointestinal Stopping Criteria

Subjects experiencing Grade 3 or Grade 4 AEs (confluent pseudomembranes or ulcerations OR mucosal bleeding with minor trauma; tissue necrosis OR diffuse spontaneous mucosal bleeding OR life-threatening consequences, e.g., aspiration, choking) will be followed as appropriate until resolution of the AE(s).

Furthermore, subjects who experience diarrhoea or enteritis should be evaluated with additional fecal occult blood tests and stool cultures as deemed appropriate by the investigator as outlined in [Appendix 8](#) and [Appendix 9](#).

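### The QTc rule removes the subject from the study rather than from treatment, so a trigger at 2 h or later in Groups A-E prevents no dosing but leaves the remaining PK samples and scheduled ECGs no longer required

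*Protocol*

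**What the plan says.** Protocol Section 5.4.2 sets two triggers, QTcF above 500 msec and a QTc change from baseline above 60 msec, with higher limits for some subjects with bundle branch block. The consequence is: "A subject who meets either of the bulleted criterion below will be withdrawn from the study".

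The neighbouring rules do not end participation in those terms.
- Liver (Section 5.4.1): "Study treatment will be stopped if the following liver chemistry stopping criterion is met". The section adds that rules about continued dosing do not really apply to a single dose, and turns to work-up and monitoring.
- GI and rash (Sections 5.4.3 and 5.4.4): the subject is followed until the event resolves. The GI entry in the risk table (Section 4.6.1) says that subjects with Grade 3 or 4 events "will have permanent discontinuation of the investigational medication and will be followed as appropriate until resolution of the AE".

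Groups A-E get one 750 mg infusion over 2 hours and stay in the clinic to Day 3. Postdose ECGs are at 1.5, 2, 4, 8, 12, 24, 36 and 48 h, and blood and urine sampling runs to 48 h (Table 3). The Follow-up/Early Termination column of Table 2 has an ECG, laboratory tests and AE review, but no PK sample. In Group F, dialysate is collected in Period 1 only (Table 5, footnote f).

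On replacement, Section 4.3 says: "if subjects prematurely discontinue the study, additional replacement subjects may be enrolled at the discretion of the Sponsor in consultation with the investigator". SAP Section 9.5.1 uses whatever data withdrawn subjects have provided; it does not ask for more.

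**The concern.** A stopping rule should stop exposure. Here, from 2 h on in Groups A-E, there is no exposure left to stop, and what ends is data collection. The timing is unhelpful. On the QT effect, Section 4.6.1 reports: "The QT prolongation evolved during the infusion and was quickly reversed over 2 hours after the end of the infusion". A drug-related trigger is therefore most likely around the end of infusion, when most of the PK profile is still to come.

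Neither document requires PK sampling or the serial ECGs to continue after a QTc withdrawal, and Section 7 allows no waivers except for immediate safety concerns. At stake are primary endpoints: AUC(0-∞), Ae total, fe% and CLr, and in Group F also CLD and Frem%(0-4). The loss would also not be random. It would fall more readily on subjects with high exposure or a long baseline QTc, in groups planned at about 8.

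**Working it through.** **1. What a 2 h trigger leaves undone (Table 3).** Of 14 postdose blood samples, the 9 from 2.5 to 48 h remain; of 8 postdose ECGs, the 6 from 4 to 48 h remain. For impaired subjects the first urine interval is 0 to 6 h, so not even one interval is complete. Without a terminal phase, λz and hence AUC(0-∞) cannot be derived. Only the 1.5 h ECG comes early enough to spare drug (the last half hour).

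**2. How much of AUC(0-∞) is unobserved at each trigger time, severe group.** Inputs from protocol Table 1: simulated Cmax 7.93 µg/mL and AUC(0-t) 28.9 µg·h/mL, the latter taken as AUC(0-∞).
- CL = 750/28.9 = 25.95 L/h; infusion rate = 750/2 = 375 mg/h.
- One-compartment model: solving (375/CL)(1 − exp(−2CL/V)) = 7.93 gives V = 65.2 L and k = CL/V = 0.398 per h.
- Unobserved share after time T = (7.93/k) × exp(−k(T − 2))/28.9.
- Two-compartment models were fitted to the same Cmax and AUC, with assumed Vss 91-130 L and central volume 25-55 L.

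| Trigger time | One-compartment | Two-compartment |
|---|---|---|
| 2 h | 69.0% | 59.9-67.3% |
| 4 h | 31.1% | 34.2-39.9% |
| 8 h | 6.3% | 14.6-24.9% |
| 12 h | 1.3% | 7.4-15.6% |
| 24 h | 0.0% | 0.7-5.2% |

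The loss matters for triggers at about 2 to 8 h and little from 24 h on.

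**3. Precision.** Half width = exp(t(0.95, n1+n2−2) × SD × √(1/n1 + 1/n2)) − 1, with AUC(0-∞) CV 27.4% (Section 9.2.1).
- Plan's figure, 16 vs 8: stated 22.75%. With SD = √ln(1 + 0.274²) = 0.2691: 1.7171 × 0.2691 × 0.4330 = 0.2001, giving 22.15%. With SD = 0.274: 22.60%. Both are within 3% (relative) of the stated value.
- One impaired subject lost, 16 vs 7: 1.7207 × 0.2691 × 0.4532 = 0.2098, giving 23.34% (SD = 0.274: 23.82%).
- Three-group ANOVA with pooled variance (16, 8, 8; then one lost): 21.9% to 23.1%.

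**4. Worst-case shift.** If the one subject lost is always the most exposed of 8, the expected maximum of 8 standard normals is 1.424. The group geometric mean changes by exp(−1.424/7 × 0.2691) − 1 = −5.3%, or −5.1% with the 26% CV of Table 1. Against a predicted severe/normal AUC ratio of 28.9/17.5 = 1.65, that gives about 1.56.

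**5. How close subjects are to the limit.** Under exclusion criterion 17, a normal subject is excluded above 450 msec, and the impaired limit reads "subject with renal impairment has a baseline QTcF of >480 msec". Distance to 500 is therefore at least 500 − 450 = 50 msec for normal subjects but can be as little as 500 − 480 = 20 msec for impaired subjects (bundle branch block with baseline 450 to 480 excepted; limit 530). For scale, take 12 msec at 1000 mg and 22 msec at 1800 mg (Section 4.6.1), with Cmax scaled by dose from 5.65 at 750 mg (7.53 and 13.56). Linear interpolation to 7.93 gives 12 + (7.93 − 7.53) × 10/(13.56 − 7.53) ≈ 12.7 msec, which alone does not reach 500 even from 480.

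**6. Group F.** The 2 h ECG is taken after the infusion and dialysis starts at about that time. A Period 1 trigger then puts 1 of only 4 to 8 dialysate data sets at risk.

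**The case against.** The strongest reply is size. No trigger rate is given, the extrapolated mean effect is well short of either threshold, replacement is allowed, group sizes are approximate and endpoints are reported as data permit. All of this stands. Replacement restores numbers, though, not the lost profile, and it does not correct a loss related to exposure or baseline QTc.

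The contrast with the other rules should not be overdrawn. The GI and rash rules require event follow-up; they do not themselves secure PK sampling. Nor does Section 5.4 draw a deliberate line between leaving treatment and leaving the study. It says "A subject may withdraw from study treatment at any time at his/her own request" and then speaks of withdrawing from the study without defining either term. The contrast shows only that Section 5.4.2 is alone in naming study withdrawal as the consequence.

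A reader might infer that a triggered subject is left without cardiac follow-up. The documents do not support that. Early Termination includes an ECG, AEs of special interest are followed to resolution (Section 7.3.1.3), further QTc readings are foreseen (Section 7.3.5), safety time points may be added (Section 7.3), and the investigator must arrange supplemental measurements for an AE (Section 12.5.5). What is not secured is the scheduled ECG series and any PK.

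A cautious consequence for a cardiac signal is defensible where dosing remains: the last half hour of infusion and Period 2 in Group F. Withholding Period 2 is a proper effect of the rule.

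Finally, keeping a subject whose infusion was cut short at 1.5 h creates a partial-dose profile. The ANOVA uses AUC and Cmax without dose normalisation, and the SAP has no rule for this case. That objection is right, and the fix has to answer it.

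**Conclusion.** The point holds as a small defect in a stated rule. From 2 h on in Groups A-E, study withdrawal protects nobody from dosing and puts primary PK data at risk in a subject who is still confined. The most likely case is a trigger at 2 h. One loss among 8 without replacement costs about 1.2 percentage points of half width, and at worst about 5% in the group geometric mean. The number of subjects affected cannot be estimated from the documents, and triggers should be uncommon.

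Two stronger readings fail. The protocol does not forbid further sampling; it merely ceases to require it. Nor should the result be a biased AUC(0-∞) for the individual. The PK Parameter Population admits only usable parameters, SAP Section 7.1.3.2 asks for well-defined profiles, and %AUCex is derived, so the value would be missing. Cmax is mostly safe: the ECG precedes the blood draw at the same nominal time, but Section 7 asks that the draw still occur on time, so Cmax is at risk only if the 2 h sample is not taken.

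The unobserved-AUC shares rest on simulated Table 1 values and assumed volumes. The QTc scaling assumes linearity in Cmax and uses data from healthy volunteers. The case for acting rests on the low cost of the change, not on a large expected loss.

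**What to change.** Keep the thresholds. In protocol Section 5.4.2, replace the consequence with wording such as:

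> A subject who meets either criterion is discontinued from study treatment (any remaining infusion, and Period 2 for Group F) but remains in the study for the scheduled PK blood and urine, dialysate (Group F), ECG and safety assessments to 48 h and the Follow-up Visit, unless consent is withdrawn or the investigator judges it unsafe.

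Add one line to SAP Section 7.1.3.2: profiles from an incomplete infusion are listed, with CL and fe% based on the dose actually given; AUC and Cmax from them are excluded from the ANOVA and regression of full-dose profiles.

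The cost is a protocol amendment with ethics review and one SAP line. No samples or visits are added. The burden is that a few affected subjects complete sampling for which they are already scheduled.

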5.4.3. Gastrointestinal Stopping Criteria

Subjects experiencing Grade 3 or Grade 4 AEs (confluent pseudomembranes or ulcerations OR mucosal bleeding with minor trauma; tissue necrosis OR diffuse spontaneous mucosal bleeding OR life-threatening consequences, e.g., aspiration, choking) will be followed as appropriate until resolution of the AE(s).

Furthermore, subjects who experience diarrhoea or enteritis should be evaluated with additional fecal occult blood tests and stool cultures as deemed appropriate by the investigator as outlined in [Appendix 8](#) and [Appendix 9](#).

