12.5.5. Evaluating Adverse Events and Serious Adverse Events

Assessment of Intensity

The investigator will make an assessment of intensity for each AE and SAE reported during the study according to the US National Institute of Allergy and Infectious Diseases DMID criteria for toxicity assessment ([Appendix 6](#)).

An event is defined as “serious” when it meets at least one of the predefined outcomes as described in the definition of an SAE (Section [12.5.2](#)).

Assessment of Causality

- The investigator is obligated to assess the relationship between study treatment and the occurrence of each AE/SAE.
- A “reasonable possibility” is meant to convey that there are facts, evidence, or arguments to suggest a causal relationship, rather than a relationship cannot be ruled out.
- The investigator will use clinical judgment to determine the relationship.
- Alternative causes, such as natural history of the underlying diseases, concomitant therapy, other risk factors, and the temporal relationship of the event to the study treatment will be considered and investigated.
- The investigator will also consult the IB and/or Product Information, for marketed products, in the determination of his/her assessment.

- For each AE/SAE the investigator **must** document in the medical notes that he/she has reviewed the AE/SAE and has provided an assessment of causality.
- There may be situations when an SAE has occurred and the investigator has minimal information to include in the initial report to GSK. However, **it is very important that the investigator always make an assessment of causality for every event prior to the initial transmission of the SAE data to GSK.**
- The investigator may change his/her opinion of causality in light of follow-up information, amending the SAE data collection tool accordingly.
- The causality assessment is one of the criteria used when determining regulatory reporting requirements.

Follow-up of Adverse Events and Serious Adverse Events

- The investigator is obligated to perform or arrange for the conduct of supplemental measurements and/or evaluations as may be indicated or as requested by GSK to elucidate as fully as possible the nature and/or causality of the AE or SAE.
- The investigator is obligated to assist. This may include additional laboratory tests or investigations, histopathological examinations or consultation with other health care professionals.

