- Standardized and commonly used toxicity tables (Division of AIDS [DAIDs], National Cancer Institute’s Common Toxicity Criteria, and World Health Organization) have been adapted for use by the DAIDs and modified to better meet the needs of participants in Division of Microbiology and Infectious Diseases trials.
- For parameters not included in the following Toxicity Tables, sites should refer to the “Guide for Estimating Severity Grade” located above.
- Criteria are generally grouped by body system.
- Some protocols may have additional protocol specific grading criteria, which will supersede the use of these tables for specified criteria.

HEMATOLOGY				
	Grade 1	Grade 2	Grade 3	Grade 4
Hemoglobin	9.5 to 10.5 mg/dL	8.0 to 9.4 gm/dL	6.5 to 7.9 gm/dL	<6.5 gm/dL
Absolute neutrophil count	1000 to 1500 /mm ³	750 to 999 /mm ³	500 to 749 /mm ³	<500 /mm ³
Platelets	75,000 to 99,999 /mm ³	50,000 to 74,999 /mm ³	20,000 to 49,999 /mm ³	<20,000 /mm ³
White Blood Cells	11,000 to 13,000 /mm ³	13,000 to 15,000 /mm ³	15,000 to 30,000 /mm ³	>30,000 or <1000 /mm ³
% Polymorphonuclear leukocytes + band cells	>80%	90 to 95%	>95%	N/A
Abnormal Fibrinogen	Low: 100 to 200 mg/dL High: 400 to 600 mg/dL	Low: <100 mg/dL High: >600 mg/dL	Low: <50 mg/dL High: N/A	Fibrinogen associated with gross bleeding or with disseminated coagulation
Fibrin Split Product	20 to 40 mcg/mL	41 to 50 mcg/mL	51 to 60 mcg/dL	>60 mcg/dL
Prothrombin Time	1.01 to 1.25 × ULN	1.26 to 1.5 × ULN	1.51 to 3.0 × ULN	>3 × ULN
Activated Partial Thromboplastin	1.01 to 1.66 × ULN	1.67 to 2.33 × ULN	2.34 to 3 × ULN	>3 × ULN
Methemoglobin	5.0 to 9.9%	10.0 to 14.9%	15.0 to 19.9%	>20%

N/A = not applicable; ULN = upper limit of normal.

CHEMISTRIES				
	Grade 1	Grade 2	Grade 3	Grade 4
Hyponatremia	130 to 135 mEq/L	123 to 129 mEq/L	116 to 122 mEq/L	<116 mEq/L or abnormal sodium with mental status changes or seizures
Hypernatremia	146 to 150 mEq/L	151 to 157 mEq/L	158 to 165 mEq/L	>165 mEq/L or abnormal sodium with mental status changes or seizures
Hypokalemia	3.0 to 3.4 mEq/L	2.5 to 2.9 mEq/L	2.0 to 2.4 mEq/L or intensive replacement therapy of hospitalization required	<2.0 mEq/L or abnormal potassium with paresis, ileus, or life-threatening arrhythmia
Hyperkalemia	5.6 to 6.0 mEq/L	6.1 to 6.5 mEq/L	6.6 to 7.0 mEq/L	>7.0 mEq/L or abnormal potassium with life-threatening arrhythmia

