Vomiting	1 episode in 24 hours	2 to 5 episodes in 24 hours	>6 episodes in 24 hours or needing IV fluids	Physiologic consequences requiring hospitalization or requiring parenteral nutrition
Constipation	Requiring stool softener or dietary modification	Requiring laxatives	Obstipation requiring manual evacuation or enema	Obstruction or toxic megacolon
Diarrhoea	Mild or transient; 3 to 4 loose stools/day or mild diarrhoea lasting <1 week	Moderate or persistent; 5 to 7 loose stools/day or diarrhoea lasting >1 week	>7 loose stools/day or bloody diarrhoea; or orthostatic hypotension or electrolyte imbalance or >2L IV fluids required	Hypotensive shock or physiologic consequences requiring hospitalization
Oral discomfort/ Dysphagia	Mild discomfort; no difficulty swallowing	Some limits on eating/drinking	Eating/talking very limited; unable to swallow solid foods	Unable to drink fluids; requires IV fluids

IV = intravenous.

NEUROLOGICAL				
	Grade 1	Grade 2	Grade 3	Grade 4
Neuro-Cerebellar	Slight incoordination dysdiadochokinesis	Intention tremor, dysmetria, slurred speech; nystagmus	Locomotor ataxia	Incapacitated
Psychiatric	Mild anxiety or depression	Moderate anxiety or depression; therapy required; change in normal routine	Severe mood changes requiring therapy; or suicidal ideation; or aggressive ideation	Acute psychosis requiring hospitalization; or suicidal gesture/attempt or hallucinations
Muscle strength	Subjective weakness; no objective symptoms/signs	Mild objective signs/symptoms; no decrease in function	Objective weakness; function limited	Paralysis
Paresthesia (burning, tingling, etc.)	Mild discomfort; no treatment required	Moderate discomfort; non- narcotic analgesia required	Severe discomfort; or narcotic analgesia required with symptomatic improvement	Incapacitating; or not responsive to narcotic analgesia
Neurosensory	Mild impairment in sensation (decreased sensation, e.g., vibratory, pinprick, hot/cold in great toes) in focal area or symmetrical distribution; or change in taste, smell, vision, and/or hearing	Moderate impairment (moderately decreased sensation, e.g., vibratory, pinprick, hot/cold to ankles) and/or joint position or mild impairment that is not symmetrical	Severe impairment (decreased or loss of sensation to knees or wrists) or loss of sensation of at least moderate degree in multiple different body areas (i.e., upper and lower extremities)	Sensory loss involves limbs and trunk; paralysis; or seizures

MUSCULOSKELETAL				

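### Section 5.4.3 restates the GI stopping rule of 4.6.1 without the stop, and with Grade 3/4 wording that conflicts with the DMID tables

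*Protocol*

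**What the plan says.** Three parts of the protocol bear on a severe gastrointestinal event.

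- **Section 4.6.1 (Risk Assessment)** states the rule, under its subject stopping criteria for GI effects: "Subjects experiencing Grade 3 or Grade 4 AEs will have permanent discontinuation of the investigational medication". It adds follow-up until the event resolves.
- **Section 12.5.5** sets the grading scale. The investigator grades every AE by the "US National Institute of Allergy and Infectious Diseases DMID criteria for toxicity assessment", reproduced in Appendix 6.
- **Section 5.4.3 (Gastrointestinal Stopping Criteria)** takes up the same subject. It speaks of "Grade 3 or Grade 4 AEs (confluent pseudomembranes or ulcerations OR mucosal bleeding with minor trauma", continues with tissue necrosis and diffuse spontaneous bleeding, and ends: "life-threatening consequences, e.g., aspiration, choking) will be followed as appropriate until resolution of the AE(s". A second paragraph asks for stool work-up in subjects with diarrhoea or enteritis and points to Appendices 8 and 9.

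For rash, 4.6.1 lists Grade 3 or higher, or Grade 2 with systemic involvement, under subject stopping criteria. Section 5.4.4 repeats those triggers and again gives only follow-up.

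By section 4.2, Groups A to E receive one 2-hour infusion. Group F receives one on Day 1 and another on Day 8.

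**The concern.** A site will look in section 5.4 for what to do when a subject has a severe event. For GI events it finds a section headed as a stopping criterion that contains no stop, and a description of severity that differs from the scale the site has just used to grade the event.

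The event most likely to be affected is an ordinary one. Section 4.6.1 says: "Lower GI effects (soft stools, flatulence, and diarrhoea) are the most common GI-associated adverse events". If a Group F subject has DMID Grade 3 diarrhoea after the Day 1 dose, 4.6.1 rules out the Day 8 dose, but a site working from 5.4.3 alone would not read that instruction there. At stake is a second dose, which the protocol's own risk section forbids, in a subject with end-stage renal disease who has no direct benefit from the study (4.6.2). In a multi-center study, sites may also resolve the wording differently.

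**Working it through.** There is no plan figure to reproduce. The check is a comparison of texts.

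**Step 1: the action.**

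| Section | Trigger | Stated consequence |
|---|---|---|
| 4.6.1, GI effects | Grade 3 or 4 AEs | Permanent discontinuation and follow-up |
| 5.4.3, GI | Grade 3 or 4 AEs, with a parenthesis of lesions and life-threatening consequences | Follow-up; stool work-up for diarrhoea or enteritis |
| 4.6.1, rash | Grade 3 or higher, or Grade 2 with systemic involvement | Listed under subject stopping criteria; no verb |
| 5.4.4, rash | Same as 4.6.1 | Follow-up |
| 5.4.2, QTc | QTcF above 500 msec or QTc change above 60 msec | Withdrawal from the study |

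Section 5.4.2 is the clean comparator: trigger, then stopping action. Section 5.4.1 is weaker. It opens with "Study treatment will be stopped if the following liver chemistry stopping criterion is met" but then says that stopping criteria for continued dosing do not apply to single-dose studies or, in this case, to Group F. That passage concerns liver chemistry only.

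**Step 2: the definition.** Appendix 6 has five GI rows. Their Grade 3 entries, set against the parenthesis in 5.4.3:

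| DMID row | Basis of Grade 3 | In the parenthesis? |
|---|---|---|
| Nausea | Intake, IV fluids | No |
| Vomiting | Episodes in 24 hours, IV fluids | No |
| Constipation | Manual evacuation or enema | No |
| Diarrhoea | ">7 loose stools/day or bloody diarrhoea; or orthostatic hypotension or electrolyte imbalance or >2L IV fluids required" | Not named; bloody diarrhoea could be argued under mucosal bleeding |
| Oral discomfort/dysphagia | Eating, talking, swallowing | No |

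None of the five is named. Grade 4 is partly covered: Appendix 6 treats any serious or life-threatening clinical event as Grade 4, and the last item in the parenthesis fits that. In the other direction, pseudomembranes, ulcerations, tissue necrosis and mucosal bleeding with minor trauma appear in no GI row.

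**Step 3: one case followed through.** A Group F subject has 10 non-bloody loose stools a day after the Day 1 dose.

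1. By 12.5.5 and Appendix 6, 10 is more than 7, so the event is Grade 3.
2. By 4.6.1, the drug is permanently discontinued, so there is no Day 8 dose.
3. By 5.4.3 there are two readings. If the opening reference to Grade 3 or 4 governs and the parenthesis only illustrates, the event is in scope. If the parenthesis is exhaustive, the event is out of scope and only the stool work-up applies.

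Section 5.4.3 itself states no stop under either reading.

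**Step 4: does Appendix 6 settle which reading is right?** It notes that some protocols may have "additional protocol specific grading criteria, which will supersede the use of these tables for specified criteria". Section 5.4.3 does not say whether it is such a criterion, so the question stays open.

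**Step 5: reach.** Only Group F has a second dose to withhold: about 4 to 8 subjects, in an optional part. In every group, including A to E, a stop could otherwise only mean interrupting the 2-hour infusion.

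**The case against.** The strongest reply is that the stop already exists and binds. Section 4.6.1 states it in mandatory terms, section 4.6 presents that table as the mitigation strategy for this protocol, and 7.3.1.3 refers to it by number. Section 5.4.3 permits no re-dosing, so as to the action it is an incomplete restatement and not a contradiction. This stands. A reader might infer that the protocol allows a Group F subject to be dosed again after a Grade 3 GI event; read as a whole, it does not.

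A second reply is that headings carry meaning. The rash and QTc entries in 4.6.1 also give triggers under a stopping label without an action, and 5.4.3 sits under a stopping heading. This stands in part: the intent to stop can be inferred. But the sentence in 5.4.3 does state a consequence, and that consequence is follow-up.

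A third reply concerns scope. A reader might infer that 10 loose stools a day meets nothing in 5.4.3, or that 5.4.3 replaces the DMID GI grades. The first holds only if the parenthesis is exhaustive, and the section's second paragraph does name diarrhoea. The second rests on a general sentence in Appendix 6 that 5.4.3 never invokes. Both are possible readings that the text leaves open.

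Finally, other safeguards exist: the eligibility re-check on Day 7 (Table 4), exclusions 1, 2, 16 and 22, withdrawal for safety under 5.4, and a possible reduced Period 2 dose under 6.3. They are real, but each is discretionary or names no GI grade, and a reduced dose is not discontinuation.

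**Conclusion.** The inconsistency is confirmed by the text. Section 5.4.3 drops the discontinuation that 4.6.1 requires, and it describes Grade 3/4 in terms that conflict with the scale 12.5.5 prescribes. Section 5.4.4 omits the stopping action for rash in the same way.

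Its size is small. For a subject to be dosed wrongly, optional Part 2 must run, a Grade 3 or 4 GI event must follow the first Group F dose, the site must overlook 4.6.1, and the discretionary safeguards must all fail. The documents give no Grade 3 GI rate, so no probability can be put on this.

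A reader might take Group F's share of enrolment as a measure of risk. With Part 1 at 32, that share runs from 4/(32+4+8+8) = 4/52 = 7.7% (Groups D and E at 8 each) to 8/(32+8) = 8/40 = 20% (Groups D and E not enrolled). It says how many subjects have a second dose, not how many are likely to be harmed.

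Follow-up of events to resolution is secured by 7.3.1.3, and the definition of the primary PK analysis is untouched. The change is worth making because it concerns subject protection and is cheap, not because harm is likely. Confidence is high for the mismatch in the text; that a site would be misled by it is possible but not shown.

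**What to change.** In 5.4.3:

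- Define Grade 3 and 4 GI AEs by the GI rows of Appendix 6.
- Keep the mucosal descriptors as additional triggers, and say that they do not supersede those rows.
- State the action: permanent discontinuation, which in Group F means no Period 2 dose, plus follow-up to resolution.

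In 5.4.4, state the same discontinuation action for the rash criteria that 4.6.1 already lists. Adding the Appendix 6 allergic-reaction row there would go beyond the 4.6.1 rash rule; it is optional and not needed to remove the inconsistency.

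The cost is a change of wording in two short protocol sections, with no new procedures or data. It should be in place before any Group F subject is dosed.
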